All Aim 3 analyses will be done in partnership at ENRM VA and Hines VAMC. For Aim 3 effectiveness analyses, the independent variable will be group assignment (Annie or control) and all analyses will use an analyze-as-randomized intent-to-treat approach. In addition to measuring all rehospitalization, we will determine the relatedness of the rehospitalization to the index admission (relatedness defined as having COPD or CHF as a primary or secondary diagnosis on rehospitalization). Further we will assess the potential for prevention of the rehospitalization. There are several approaches to identifying potentially preventable rehospitalizations, including using software algorithms, and more rigorous manual chart/survey data reviews. We now propose to classify readmissions as possibly preventable using a gold standard review of all data from each patient. We will measure pre-post trend in urgent care utilization. For an 18-month period pre-index hospitalization and a six-to-twelve month period post-hospitalization (depending on time of

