recruitment, we propose to extract data, our primary effectiveness measure (urgent care utilization) and dates. This is a pre-post difference in differences analysis, comparing the number of urgent care utilizations per month before and after the index-hospitalization where randomization occurred. For this analysis, the outcome for each individual is a count of urgent care utilizations. We will use a count regression with the dependent variable being the post-hospitalization count of urgent care, using the pre-hospitalization count as a covariate in the model. For this outcome, we will also construct a linear regression model using the mean change in the number of urgent care utilizations by randomization group. Finally, we will conduct an interrupted time series analysis using the times of the urgent care utilization, the randomization treatment group, a marker for pre versus post-index hospitalization. In this model, we will look for a significant difference in change in the slope of urgent care utilizations pre-post-index hospitalization by randomization group. We will evaluate sustained community tenure, (number of days out of 30 days that the Veteran is in their own home (as opposed to inpatient or in the emergency department). For this measure, we will first explore the distribution of the outcome to assess whether it fits best as a count distribution or a difference in mean proportion of days. We will then conduct a bivariate analysis with the dependent variable (sustained community tenure) and the independent variable (randomized group assignment).

Power Calculations:

For our primary outcome measure, we first estimated a mean number of urgent care visits (ED and hospitalization) for the six months pre-randomization and six months postrandomization for each patient. We know that readmission rates are between 12.7% and 21% annually for our Veterans, and ED visits will be similar or higher per year (thus urgent care use = 25%-40%). Thus, we estimate a monthly rate of urgent care use of 3% (40% annual/12 months) of our sample of 600 patients (thus a mean of 18 utilizations per month). Using a pre-intervention rate of 18 for both intervention and control, and a postcontrol change of 1, assuming an alpha of 0.05, and we have power (0.8) to detect a difference of differences in change in mean urgent care utilization of 0.75 with a standard deviation equal to the control mean.

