Our recruitment will occur over 24 months, post-discharge number of months of data will vary between six and twelve, and will extend back in time for up to 24 months, resulting in a total number of months between 24 and 36 for urgent care utilization. With these assumptions, we are powered to detect an effect size of 0.5 with an autocorrelation between 0.0 and 0.2.

Assuming a baseline rate of 1.0 and the mean exposure time to be 30 days, a sample of 300 patients in each group will achieve 80% power at a two-sided alpha level of 0.05 to detect a rate ratio of at least 1.0425. This calculation is based on a Poisson Regression with the number of 30-day sustained community tenure counts as the dependent variable and randomized group as a binary independent variable.

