4.6 Risk/Benefit Ratio

4.6.1 Potential Risks and Methods to be Used to Minimize Risks:

The risks of the study are minimal. Risks to participants relate mostly to misinterpretation of what is research and loss of confidentiality. The major risk is the accidental disclosure of information; however, every precaution will be taken to prevent this from occurring. Our study team has had direct experience with data loss, and we have developed a strong culture of secure, detailed operating procedures, and are hyper vigilant of protection of confidential data. In no way will individual participant data be released to the public or cited in a publication.

All data will be coded with a patient code (for example, patient001). Any hardcopy files will be stored in locked file cabinets at each respective site. A file stored separately from the data will contain participant identifiers and codes. All recordings will be stored on a secure server located at each site. Data for analyses will be stored at the Bedford ENRM VA Hospital behind the VA firewall. In an access-restricted folder on network servers maintained by a dedicated CHOIR IT specialist. Server v01.med.va.gov Q:\DATA\[name] TACT CHF COPD IIR. All computers are password protected and all computers on which data analysis will be done are encrypted using VA authorized encryption software. Study personnel including investigators, project coordinator, research assistants, discharge assistants, and data analyst will have access to data/codes. All recordings will be transcribed. Transcription will be done by a certified transcription service which meets all VA security standards.

There may be some stress involved in patients describing their care transition experience, learning how to use the Virtual Nurse, and for the healthcare providers to be observed in their care transition support activities, but we will emphasize that this participation is voluntary.

Any hospitalizations or deaths discovered by the research team will be promptly reported to IRB with an assessment of whether any study procedures may have contributed to these outcomes.

4.6.2 Data and Safety Management Plan:

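### The urgent care count model has no time-alive term and deaths are not compared by arm, so a mortality difference could shift the ratio either way unseen

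*Combined protocol and SAP*

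**What the plan says.** Section 1.0 (Aim 3) takes lower urgent care use under Annie as the trial's hypothesis. Section 3.5 describes the analysis as "comparing the number of urgent care utilizations per month before and after the index-hospitalization", but then says that "the outcome for each individual is a count of urgent care utilizations". The count regression has "the dependent variable being the post-hospitalization count of urgent care, using the pre-hospitalization count as a covariate in the model". Two further analyses follow: "a linear regression model using the mean change in the number of urgent care utilizations by randomization group", and an interrupted time series. None of the three states an offset, a censoring rule or a treatment of time after death.

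Follow-up is unequal by design: "post-discharge number of months of data will vary between six and twelve". Patients who die stay in the comparison, because "all analyses will use an analyze-as-randomized intent-to-treat approach".

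Date of death is requested from the Vital Status File (Section 3.4, list of data elements), yet no analysis in Section 3.5 uses it. That section compares rehospitalization, urgent care, community tenure and cost, but not death. Elsewhere deaths appear as individual reports. Section 4.6.1 says that "deaths discovered by the research team will be promptly reported to IRB with an assessment of whether any study procedures may have contributed", and Sections 4.1 and 4.6.2.2 require immediate IRB notification. Section 4.6.2.1 adds a summary of adverse events sent by site investigators to the principal investigator. None of these is stated to be by arm.

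**The concern.** A Veteran who dies in month two has four to ten months in which no urgent visit can occur. In a model of the raw count, those months look the same as months spent well at home. Against that, a death may be preceded by an ED visit or admission that would not otherwise have happened, which raises the count. A difference in deaths between arms can therefore push the urgent care ratio down or up, depending on which effect is larger.

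What is at stake is how the main result is read. A reader shown fewer urgent visits under Annie needs to know whether similar numbers in each arm were alive to make them. If Annie prevented deaths and few deaths were preceded by an extra visit, the raw count would make it look slightly worse than it is. Individual IRB review is not designed to show a difference between arms.

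**Working it through.** The plan prints no figure that this point disputes, and its power calculation has no mortality input. The check asks how far unequal deaths move the ratio when Annie has no effect on the urgent care rate while alive.

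**Inputs from the protocol (Section 3.5).** 300 per arm; 3% urgent care use per patient per month (18/600 = 0.03); 6 to 12 months of follow-up; 18 months of pre-index data.

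**Assumed inputs.** All mortality inputs: six-month death risk d; a frail 40% who die at 3 times the risk of the others and use urgent care at k = 1, 3 or 5 times their rate; deaths on average at mid-window; a share t of deaths bringing one extra visit.

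**Closed form, window W months.** With r = 0.03/(0.6 + 0.4k), dn = d/1.8 and df = 3dn:

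count = 0.6r(W - dn·W/2) + 0.4kr(W - df·W/2) + d·t

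For k = 1, t = 0, W = 6 this is 0.18(1 - d/2). That gives 0.1710 at d = 0.10 and 0.1665 at d = 0.15, a ratio of 0.974. Results for k = 1 / 3 / 5 at W = 6:

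| Deaths, control v Annie | t | Ratio, Annie/control |
|---|---|---|
| 10% v 10% | 0 | 1.00 |
| 10% v 12% | 0 | 0.989 / 0.986 / 0.985 |
| 10% v 15% | 0 | 0.974 / 0.965 / 0.962 |
| 10% v 20% | 0 | 0.947 / 0.931 / 0.924 |
| 15% v 10% | 0 | 1.027 / 1.036 / 1.039 |
| 10% v 15% | 0.5 | 1.093 / 1.088 / 1.086 |

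**Where the direction changes (10% v 15%).** The ratio is 1.00 when t equals the count lost at t = 0 divided by the difference in deaths. For k = 1 and W = 6 this is (0.1710 - 0.1665)/0.05 = 0.09. Across k = 1 to 5 it is 9-13% of deaths at six months and 13-19% at nine months.

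**Simulation of the count model.** 1,500 trials per row; follow-up uniform over 6-12 months; exponential death times set by the six-month risk; pre-count over 18 months as covariate; Poisson regression with robust standard errors. Deaths continue after month six, so shifts without the offset at t = 0 are somewhat larger than in the closed form. Entries are k = 1 / k = 3.

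| Six-month deaths; t | Ratio, no offset | Ratio, log time-alive offset | Significantly favours Annie: no offset | With offset |
|---|---|---|---|---|
| 10% v 10%; 0 | - | - | 2.7% / 2.2% | - |
| 10% v 15%; 0 | 0.956 / 0.938 | 0.998 / 0.982 | 4.7% / 5.1% | 2.1% / 2.9% |
| 10% v 20%; 0 | 0.915 / 0.884 | 0.999 / 0.968 | 7.7% / 10.4% | 2.6% / 4.5% |
| 10% v 15%; 0.5 | 1.076 / 1.065 | 1.123 / 1.113 | - | - |

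In the last row, significant results against Annie rise from about 5-8% to 9-13% when the offset is added.

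**Scale.** Expected control events are 300 × 0.03 × 6 = 54, or 81 at nine months. Solving -ln R = 2.80·√(1/E + 1/(E·R)) gives a detectable ratio of about 0.52 (E = 54) or 0.60 (E = 81).

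**Precision of a death comparison.** The 95% half-width is 1.96·√(p0(1-p0)/300 + p1(1-p1)/300). It is 5.3 points at 10% v 15% (power 46%) and 3.1 points at 3% v 5%. The hazard ratio at 10% v 15% is ln 0.85/ln 0.90 = 1.54, with standard error √(1/30 + 1/45) and interval 0.97-2.45. With 30 deaths in each arm it is 1.0 (0.60-1.66).

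**The case against.** **A rate is already implied.** Comparing 18 months before with 6-12 months after only makes sense per month, so a rate was probably intended. That is fair. But the denominator is never defined or carried into a model, and a calendar-month denominator would still count months after death as event-free.

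**Randomization balances follow-up.** Administrative follow-up depends on recruitment date, and randomization in blocks within site should balance it. This stands: the 6-12 month spread is not itself a source of bias between arms. Deaths after randomization carry no such guarantee.

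**The effect is small and nothing suggests it.** The comparison is tablet education and texts against an active control, on top of unchanged care. The documents give no reason to expect 50% or 100% more deaths under Annie. This also stands and limits the weight of the point. Section 3.4 does, however, set a goal of evaluating safety and clinical risks of the texting component.

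**The offset can make matters worse.** If deaths differ and are often preceded by urgent visits, the offset moves the ratio further from 1. The last simulation row confirms this, so the offset cannot be offered as a cure.

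**The death table will be imprecise, and dates allow one later.** Both are true. The gap is that nothing commits the investigators to the table before the result is known.

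**Conclusion.** The point holds as a gap in specification with a modest effect. The count model has no exposure term, date of death is obtained but not used in any listed analysis, and a mortality difference would pass unseen. At an assumed 10% v 15%, the ratio shifts to about 0.94-0.97 with no extra visits and to about 1.07-1.09 if half of deaths bring one. It is 1.00 when deaths are balanced. Every mortality input is an assumption.

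A reader might infer more than this. The documents do not support the following readings:

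- **Deaths would flatter Annie.** The direction reverses once about 10-20% of deaths bring an extra visit, and the documents say nothing about that share.
- **Deaths could produce a false positive trial.** Shifts of this size are far from the detectable ratio of 0.52-0.60, so deaths would seldom create significance alone.
- **Deaths are unmonitored.** They are reported individually to the IRB, and adverse events are summarized for the principal investigator. What is missing is a stated comparison by arm.
- **Community tenure shares the defect.** It is the "number of days out of 30 days that the Veteran is in their own home", which read literally already scores days after death as zero.

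**What to change.** 1. In Section 3.5, add all-cause death by randomized arm from the Vital Status File, for all randomized Veterans. Give the 30-day risk difference and the hazard ratio through each patient's follow-up, with 95% confidence intervals. Report these beside the urgent care result, labelled a safety estimate and not a powered test.
2. In the count model, add the log of observed time alive (discharge to the earlier of death or end of data) as the offset, so that the monthly rate means per month alive and observed. Use the same denominator in the linear change and interrupted time series models. Present the estimate as a rate while alive, to be read with item 1.

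The cost is one table and one offset term with matching denominators, from data already requested. No new patients, visits, staff or committee are needed, and IRB reporting stays as it is. There are two downsides to state in the plan. The mortality interval is wide (about 5 points either way at 10-15% mortality), so a non-significant difference is not evidence of safety. And if deaths differ and are often preceded by urgent visits, the offset moves the ratio further from 1, so it must not be read without the death table.

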At the four study sites (Boston, Iowa City, Hines, Palo Alto), this hybrid Type 1 randomized trial “The Annie intervention” is targeted primarily at patients and not clinical units so randomization is at the patient level. We will also collect data about various cluster-level factors to evaluate variations in implementation, and will incorporate in our data models as random effects.

As in the pre-implementation pilot, patients from the four sites will be randomized to the full Annie intervention (onscreen inpatient and texting outpatient), or the active comparison control. Informed consent will explain to the patients that they will receive one of two interventions to support their transition back to home.

After consent and baseline surveys at the four sites, Veterans will be randomized. The randomization program will use a randomization table using a permuted block design (block sizes of five) developed by our statistician. Each VHA site will have a separate randomization table. As all patients receive some intervention (active control or Annie), they will remain blinded to group assignment. Veterans randomized to Annie or control in the pilot experiment will be re-contacted seven days post-discharge to assess the Care Transition Measure. Feedback to inform the refinement of Annie’s interface and content will be gathered through interviews conducted with Veterans immediately after exposure to the Annie interface. Interviews will address challenges with the touch screen and display, organization of content displayed, and clarity of instructions and feedback that Annie provides. This information will be used to inform iterative rounds of interface modifications. In our Aim 1 work, we are interested in understanding the usability experiences of Veterans with CHF and COPD. Thus, ten Veterans (five with CHF and five with COPD) will be recruited for interviews.

The following table is a map describing each of the measures and when they will be utilized.

#	Measure/Instrument	Phase/Timing and Description
SECTION A: Baseline		
1	Trial Baseline Questionnaire	At baseline of the testing for all participants
SECTION B: Immediate Post-Exposure		
2a/b	Trial Tablet/Agent Usability Questionnaires	Testing for the tablet component, questions flagged for intervention vs. control after interaction with the tablet
SECTION C: 7-Day Outcomes		
3	7 Day Post Discharge Care Transition Measure	At 7 days post discharge
SECTION D: 30-Day Outcomes		

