4.2 Inclusion of Vulnerable Subjects and Special Populations

Participants from the four sites will be identified through daily census lists of hospital units. Our primary inclusion criteria are that Veterans have to have a diagnosis of CHF or COPD, be admitted to a general medical service and be able and willing to engage with the touchscreen. For the trial, patients will also be required to have access to a text-enabled cellular phone to receive the post-discharge text messages. Enrollment begins with the person facilitating enrollment initiating contact with the patient in their hospital room (most rooms are private rooms, and we will limit recruitment to patients in these rooms). The person facilitating enrollment at each site over the total 24 month enrollment period will be our “discharge assistants” who play the role of a centralized discharge facilitator and are funded by the grant. Consent and randomization will again follow protocols from Aim 1

Sub-Aim A. Randomization will be stratified by condition (CHF or COPD) to assure balance on this key variable. As all patients receive some intervention (active control or virtual nurse), they will remain blinded to group assignment. After discharge, patients will be re-contacted by study personnel at seven and 30 days to conduct follow-up assessments as detailed in D.3 (Aim 3).

Children are not included.

The research topic is focused on adult veterans hospitalized for congestive heart failure and/or chronic obstructive pulmonary disease, which may include women or minorities. We feel it is important to ensure adequate representation of women and minorities in this study. As such, we propose to oversample minorities with a goal of filling 20% of the sample. We will also prioritize recruitment of women Veterans into the study; recognizing that many women Veterans are younger and as such, may be less likely to have CHF or COPD diagnoses.

The clinical leadership and inpatient clinical team members may also include women, pregnant women, and minorities, but not children.

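### The count and community-tenure models leave out the factors used at randomization (reported SE about 0%–2% too large, no bias), and 200 per site at four sites gives 800, not 600

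*Combined protocol and SAP*

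**What the plan says.** **Randomization.** Section 4.2 states: "Randomization will be stratified by condition (CHF or COPD) to assure balance on this key variable". Section 3.4 adds: "Each VHA site will have a separate randomization table". The blocks are of five.

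**Effectiveness models (section 3.5).** There are four:
- A count regression of post-hospitalization urgent care on group, "using the pre-hospitalization count as a covariate in the model".
- A linear model: "we will also construct a linear regression model using the mean change in the number of urgent care utilizations by randomization group".
- An interrupted time series "using the times of the urgent care utilization, the randomization treatment group, a marker for pre versus post-index hospitalization".
- For community tenure, a "bivariate analysis with the dependent variable (sustained community tenure) and the independent variable (randomized group assignment".

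In the effectiveness part of section 3.5, CHF and COPD appear only in the definition of a related rehospitalization. For site, the nearest text is in section 3.4: cluster-level factors, collected to evaluate variation in implementation, are ones the team "will incorporate in our data models as random effects".

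**Sample size.** Section 3.3 b sets a target of 600 Veterans, puts it at 200 per site, and names four sites in the same sentence. The total of 600 recurs in that section's Medicare request and in sections 3.5, 4.1, 4.5 and 4.5.1. The tenure power statement uses 300 per group.

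**The concern.** A factor important enough to stratify on normally also enters the analysis. Stratification makes the arms more alike than simple randomization would. An SE that ignores the strata, if it is estimated from the residual spread, does not register that gain and comes out a little too large. The section 3.4 sentence does not close the gap: condition is a patient-level factor, and the sentence ties site to no outcome model. What is at stake is a small amount of reported precision in the count and tenure analyses.

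The per-site figure is a separate matter. It contradicts the total in its own sentence, so the documents give two incompatible recruitment targets.

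**Working it through.** **1. Which sample size is the planned one?** The inputs are in the Power Calculations: baseline rate 1.0, exposure 30 days, rate ratio 1.0425, two-sided alpha 0.05, power 80%.

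n per arm = (1.960 + 0.842)² × (1/30 + 1/(30 × 1.0425)) / (ln 1.0425)² = 296, close to the stated 300. Power at 300 per arm is 80.5%. So 600 is the powered total.

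Sites: 4 × 200 = 800, which is 200 (33%) above 600. 600/4 = 150. The figure of 200 would fit three sites (600/200 = 3), but the documents do not say where it comes from.

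**2. Rough bound for condition alone in a count model, before the pre-count is added.**
- CHF share p = 1,147/(1,147 + 765) = 0.60 (section 4.5).
- Mean count m = 0.40, the top annual figure in section 3.5.
- Rate ratio r = 2.0 with COPD higher (assumed; the documents give no rates by condition).
- Lower rate a = m/(p + (1 − p)r) = 0.40/1.40 = 0.286.
- Between-condition variance = p(1 − p)(ar − a)² = 0.24 × 0.286² = 0.0196.
- SE ratio, without/with condition = √(1 + 0.0196/0.40) = 1.024.

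With r = 1.65, the spread of the plan's own readmission range (21/12.7), the ratio is 1.013. With r = 1.25 it is about 1.002.

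**3. Simulation with the pre-count in the model.**
- N = 600 in four sites of 150, with blocks of five (random majority) within eight site-by-condition strata.
- Rate 3% per month (section 3.5).
- The data window is "For an 18-month period pre-index hospitalization and a six-to-twelve month period post-hospitalization". The runs use 18 months before and 9 after (midpoint of 6–12), so means are 0.03 × 18 = 0.54 and 0.03 × 9 = 0.27.
- Assumed: condition rate ratio 1.25–2.0; highest-to-lowest site ratio 1.0–2.0.
- 4,000 null trials per setting.

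SE ratio, without/with condition and site:

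| Analysis | Poisson counts | Patient-level gamma dispersion 1 (assumed) |
|---|---|---|
| Count, dispersion-scaled SE | 1.0006–1.0191 | 1.0007–1.0116 |
| Count, robust SE | 1.0007–1.0195 | 1.0001–1.0112 |
| Count, plain Poisson SE | 0.9991–0.9993 | 0.9980–0.9985 |

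The linear change model gives 0.9992–0.9993. The time-series slope term (60 trials) gives 1.0000.

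The largest ratio in any run was 1.026 (12 months after, both ratios 2.0; 400 trials). At 2.0/2.0 with Poisson counts and the scaled SE, rejection was 4.9% without the strata and 5.3% with them. The Monte Carlo SE is √(0.05 × 0.95/4,000) = 0.34 points, so neither is distinguishable from 5%.

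A second simulation used a true rate ratio of 0.75, follow-up varying from 6 to 12 months and a different form of site variation. It gave mean robust SE ratios of 1.003–1.015. The 1.003 also appeared with no condition or site effect, so that part is not a gain. Bias in the log rate ratio was −0.009 to +0.004, nearly the same with and without adjustment (Monte Carlo SE 0.007–0.009).

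**4. Community tenure, no covariate, linear or dispersion-scaled SE.** Share of variance due to strata = λ·CV²·E[L]²/(E[L²] + λ·CV²·E[L]²), where λ is the 30-day event rate and L the days lost per event (5, assumed).
- Upper case: λ = 0.20 (section 2.1), L fixed, condition and site ratios 2.0.
- Condition CV², with CHF higher = 0.24/(0.60 × 2 + 0.40)² = 0.094. Site CV², with four sites evenly spaced on the log scale = 0.065. Together 1.094 × 1.065 − 1 = 0.165.
- Share = 0.20 × 0.165 × 25/(25 + 0.20 × 0.165 × 25) = 0.032.
- SE ratio = 1/√(1 − 0.032) = 1.016.
- Lower case: λ = 0.03, condition 1.25, site 1.0, L geometric. SE ratio 1.0001.

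**5. Power.** With a 2% larger reported SE, power is Φ(2.802 − 1.96 × 1.02) = 78.9% instead of 80%.

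**The case against.** The best case for the plan is that almost nothing follows from the omission. Section 3.3 b notes that randomization is within site and expects site differences to balance. The pre-count and the change scores absorb much of any stable difference. Two of the four models gain nothing from the extra terms, and the upper figures need rate ratios of 2.0 for both condition and site, which are assumptions. All of this stands, and it limits the point to a small improvement in two models. It also means the cost is mainly conservatism in the reported SE: in the second simulation the actual spread of estimates hardly moved (for example 0.1605 without and 0.1603 with the strata).

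It can also be said that the random-effects sentence covers site. It may be meant to, but it names no outcome model and cannot cover condition.

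Two stronger readings are tempting and are not supported. A reader might infer that the plan leaves adjustment open until the data are seen. It does not: section 3.5 names the pre-count for the count model and calls tenure bivariate, and the only data-dependent choice it states there is the distributional form for tenure. A reader might also infer that a site enrolling 150 would be judged 25% short. Section 4.6.2.1 asks for expected against actual recruitment, but does not say that 200 is the expected figure.

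**Conclusion.** Both parts hold, at modest weight.

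(1) Leaving condition and site out of the count and tenure models makes the reported SE conservative by about 0%–2% with scaled or robust SEs (linear or scaled for tenure). That costs about one point of power at a 2% larger SE. The range rests on assumed rate ratios, dispersion and days lost per event. It is not a source of bias and does not threaten validity, provided the expected allocation ratio is the same in every stratum. Blocks of five cannot split evenly between two arms and the split is not stated, so that condition should be recorded. An unstated split is not evidence that the ratio differs between strata.

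(2) The per-site figure is wrong as written. It should not be read as a target of 800: the power calculation and every other total support 600, and no analysis depends on 200 per site.

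**What to change.** **Section 3.5.**
- Count regression: include randomized group, the pre-hospitalization count, condition as used at randomization, and site.
- Community tenure: replace the bivariate analysis with a model containing group, condition and site.
- State a dispersion-scaled or robust SE for both.
- Adding the terms to the linear change and time-series models is optional, for consistency only. Whether site is fixed or random is for the trial statistician.
- Date the change before outcomes are seen by arm. If that is no longer possible, report the adjusted results beside the unadjusted ones.
- Record the split used within blocks of five and the stratum used for patients with both diagnoses.

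**Section 3.3 b.** Replace the per-site figure with *an average of 150 per site* or *competitive enrolment to 600*. If enrolment is complete, report the actual numbers per site and arm.

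**Cost.** Text only. Condition and site are already in the data, and no further patients or measurements are needed.

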the discharge assistant and clinical teams, we will include questions about time when collecting implementation data. We will then estimate wages based on staff positions using data obtained from the facility. The economic analyses for Aim 3 will primarily consist of descriptive statistics. Using the estimates of costs of supplies, equipment, and staff time and the potential savings that result from decreased healthcare costs related to CHF and COPD, we will calculate the budget impact of implementing the intervention from the perspective of the facility. We will follow the guidelines outlined for best practices in BIA. We will create tables to describe the assumptions of our inputs and outputs, and perform sensitivity analyses to examine how changing the assumptions of the model impact the potential costs for the facility. To compare patient costs in the pre- and post-periods for the intervention and control groups, we will use GLM (generalized linear models) that accounts for the skewness in distribution of costs, and we will calculate 95% confidence intervals around differences in costs using bias corrected accelerated bootstrapping. Because there are potential issues of bias and precision, we will employ checks to select a model that is consistent and robust in the face of the skewness that is characteristic of healthcare costs.

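### The additional linear model of urgent care use compares change scores without adjusting for the pre value; baseline adjustment answers the same question at least as precisely, at no cost

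*Combined protocol and SAP*

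**What the plan says.** Section 3.5 (Analysis Plan) makes urgent care utilization the primary effectiveness measure and frames its analysis as a comparison of differences: "This is a pre-post difference in differences analysis, comparing the number of urgent care utilizations per month before and after the index-hospitalization". Three models follow.

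1. A "count regression with the dependent variable being the post-hospitalization count of urgent care, using the pre-hospitalization count as a covariate in the model".
2. The model at issue: "we will also construct a linear regression model using the mean change in the number of urgent care utilizations by randomization group". No pre value is named as a covariate.
3. An interrupted time series that compares slopes before and after the index hospitalization.

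None of the three is designated primary.

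The analysis text sets the windows: "For an 18-month period pre-index hospitalization and a six-to-twelve month period post-hospitalization". The power paragraph uses six months before and six after. The time-series power text goes back up to 24 months. The scale also varies: the framing sentence speaks of utilizations per month, while the next says "the outcome for each individual is a count of urgent care utilizations".

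**The concern.** Under patient-level randomization the expected pre value is the same in both arms. The difference in mean change and the baseline-adjusted difference in post means therefore estimate the same quantity. They differ in precision. A change score subtracts the whole pre value whatever its relation to the post value, whereas the adjusted model subtracts only the fraction that the data support.

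This matters most when the pre value is a weak predictor. At the plan's 3% per month, a six-month count averages 0.18 events (6 × 0.03), so much of its variance is chance and the pre-post correlation is likely to be low. Subtracting it can then add more noise than it removes.

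At stake is a wider confidence interval than the data require for the linear result. The plan would also hold two neighbouring models of one outcome that treat the baseline differently, with no statement of which takes precedence.

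**Working it through.** **The plan's own figure.** The plan gives no precision for the linear model. The nearest figure is "power (0.8) to detect a difference of differences in change in mean urgent care utilization of 0.75", with the SD set equal to the control mean. Taking SD 18 and 300 per arm (the per-arm number comes from the community-tenure calculation), SE = 18 × √(2/300) = 1.47 and 0.75/1.47 = 0.51. Two-sided power at 0.05 is then about 7.4%, not 80%; 80% would need an SD near 3.28. The figure does not reproduce and contains no pre-post correlation, so it cannot be used to size this point.

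**Inputs.** From the documents: rate μ = 0.03 per patient-month; windows of 18 months pre and 6 to 12 post (analysis text), or 6 and 6 (power text). Assumed, because the documents are silent: Poisson counts with patient rates that vary by a gamma factor of variance φ = 0.5 to 2, and, as a sensitivity check, higher rates of 0.1 to 0.2 per month.

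**Formulas**, for monthly rates with A months pre and T months post:

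- Var(pre) = μ/A + φμ²; Var(post) = μ/T + φμ²; Cov = φμ²
- Change score: V_c = Var(pre) + Var(post) − 2 Cov
- Baseline-adjusted: V_a = Var(post) − Cov²/Var(pre)
- Information lost = 1 − V_a/V_c. With equal windows and pre-post correlation ρ this is (1 − ρ)/2.

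V_c − V_a = (Var(pre) − Cov)²/Var(pre), which is never negative. The direction therefore does not depend on the assumptions; only the size does.

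**Worked case**, 18 v 12 months, μ = 0.03, φ = 0.5:

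- Cov = 0.00045; Var(pre) = 0.002117; Var(post) = 0.002950
- V_c = 0.004167; V_a = 0.002854
- Ratio V_c/V_a = 1.46; loss = 31.5%

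**Results on monthly rates**

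| Windows (pre v post) | Rate/month | V_c/V_a, φ = 0.5 | V_c/V_a, φ = 2 | Information lost |
|---|---|---|---|---|
| 18 v 6 | 0.03 | 1.25 | 1.14 | 20% to 12% |
| 18 v 12 | 0.03 | 1.46 | 1.24 | 32% to 19% |
| 18 v 12 | 0.1 | 1.27 | 1.10 | 21% to 9% |
| 18 v 6 | 0.2 | 1.10 | 1.03 | 9% to 3% |
| 6 v 6 | 0.03 | 1.85 | 1.58 | 46% to 37% |

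In the 6 v 6 rows ρ is 0.08 to 0.26, and the change score has 1.83 to 1.47 times the variance of the post value alone: there it does worse than ignoring the baseline.

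**Checks.** Simulation at φ = 2 and 0.03 per month gave losses of 37% (6 v 6), 13% (18 v 6) and 21% (18 v 12), against 37%, 12% and 19% by formula. With much stronger heterogeneity (φ = 10) the losses at 0.03 per month fall to 18%, 4% and 6%. If change were taken in raw counts over unequal windows, the loss at φ = 0.5 to 2 would be about 50% to 78%, so the unstated scale also matters.

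**The case against.** The strongest reply is that the plan already does what is asked. Its first-listed model adjusts the post count for the pre count, on a scale suited to counts, and the linear model is introduced as an addition. That stands, and it limits the point. A reader might infer that the trial discards its baseline information or a share of its 600 Veterans; the documents do not support that. The loss would bear on the trial's conclusion only if the linear result became the deciding one. The plan does not say so, but by naming no primary analysis it does not rule it out.

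A second reply is that the sentence does not forbid a pre-value covariate. This is correct: adding the pre value on the same scale to a model of change gives exactly the treatment estimate of the adjusted model. But no covariate is named here, and one is named for the model beside it.

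Three stronger readings also fail.

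- It is tempting to say that the primary measure's only power claim rests on the weaker analysis. Section 3.5 also gives a time-series power statement for urgent care utilization. The 0.75 statement starts from an aggregate of 18 utilizations per month and is not shown to use a patient-level change variance. Its failure to reproduce is a separate issue.
- The cost analysis might seem to share the flaw, since a generalized linear model is planned "To compare patient costs in the pre- and post-periods for the intervention and control groups". That wording commits neither to a pre/post-by-group contrast nor against baseline adjustment, and the variance formulas above are for linear models.
- Disagreement between the linear and count models could not be put down to noise alone. With a log link, the usual choice for counts, the count model estimates a ratio while the linear model estimates a difference.

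**Conclusion.** The point holds for the additional linear model only. As written it is an unadjusted change-score comparison, and the baseline-adjusted version targets the same absolute difference with a large-sample variance that is never larger.

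The size is an assumption, not a property of this trial that the documents establish. Under φ = 0.5 to 2, the analysis text's windows give a loss of about 12% to 32% at the plan's event rate and 3% to 21% at assumed rates of 0.1 to 0.2 per month. The 37% to 46% figure belongs only to the power paragraph's six-month windows at 0.03 per month. Stronger heterogeneity shrinks these losses, and raw counts over unequal windows enlarge them. This is a free improvement to one supporting model rather than a defect in the trial's main inference.

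**What to change.** Replace the sentence on the linear model with: *a linear regression of the post-period monthly rate of urgent care utilization on randomized group, with the pre-period monthly rate as a covariate and robust standard errors.* Report raw mean changes by arm as description only.

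Using monthly rates on both sides also settles whether counts or rates are meant when the windows differ. The robust standard errors allow for unequal variances, including those that come from follow-up of 6 to 12 months.

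The cost is one sentence of analysis-plan wording. The data are already to be extracted, nothing more is collected, and the quantity estimated does not change.
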